21. Baseline tumour-biopsy sample to be taken from the projected injected and one distinct non-injected lesion between screening and first administration of BI 1387446. Only patients considered eligible after assessment of inclusion/exclusion criteria will be subjected to the procedure. Refer to [Section 4.1.4.1](#), [4.1.4.2](#) and [5.4.2.3](#) for lesion selection. In patients crossing over from Arm A to Arm B after completion of Cycle 1, new baseline biopsies from the injected and non-injected lesion should be taken. If biopsy at C2D1 was obtained without further treatment following the biopsy in Arm A, this new baseline biopsy is not needed.
22. Biopsy at Cycle1/Day 1 to be optionally taken 5-24h post BI 1387446 administration from the injected lesion only from patients enrolled into Arm A.
23. Optional biopsy.
24. Tumour assessments should be done according to itRECIST, and should include computed tomography (CT) scans of the chest and abdomen and, if clinically indicated, imaging of any other known or suspected sites of disease (e.g. pelvis, brain) using an appropriate method (CT or magnetic resonance imaging [MRI]). The same radiographic procedure must be used throughout the trial. The baseline tumour assessments (CT/MRI) and should be performed ≤ 28 days prior to initiation of treatment. The first on-treatment tumour assessment will be done before treatment administration at Cycle 2 (a time window of -5 days is acceptable). Positron emission tomography (PET-CT) may be performed if clinically indicated based on tumour type, however, in this case a diagnostic-quality CT scan needs to be acquired as part of the PET-CT for RECIST measurements. The CT portion of a PET-CT can be used as the basis for RECIST measurements if the site has documented that a CT with appropriate radiation dose for diagnostic quality and IV/oral contrast was used (if not medically contraindicated). Subsequent on-treatment tumour assessments will be performed before treatment administration (a time window of -7 days is acceptable) in C4, C6, C8, C10, C13, C16, C19, C23, C27, C31 and at EOT.
25. After the individual patient's end of the trial the Investigator should report only any cancers of new histology and exacerbations of existing cancer, study treatment related SAEs and study treatment related AESIs of which the Investigator may become aware of and only via the BI SAE form, refer to [Section 5.2.7.2.1](#).

Clinical Trial Protocol

[figure not shown]

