Proprietary confidential information © 2023 Boehringer Ingelheim International GmbH or one or more of its affiliated companies

26. AEs which were ongoing at the 30dFU will be followed.
27. Consecutive biopsies should be taken always from the same lesion if clinically feasible.
28. Biopsies are taken from the projected injected and one distinct non-injected lesion if not indicated differently in the [Flow Chart](#). Mandatory timepoints are baseline and C2D1. At optional timepoints only, patients with lesions suitable for diagnostic biopsy associated with limited procedural risks should be included (refer to [Section 5.4](#) for details).
29. Sampling for ADA only in Cycles 6, 9, 12, 18, 24, 30 and 34.
30. Abbreviated physical examination (focused on the specific disease, at the Investigator's discretion).
31. After Cycle 5, every other cycle (i.e. Cycle 7, 9, 11...33).
32. Safety laboratory does not need to be repeated if the result is available within 24h prior to the drug administration.
33. No need to perform tumour assessment if it has been done within the 3 weeks prior to EoT.
34. Echocardiography will be obtained prior to administration of trial drugs (if drug administration is applicable) on Day 1 in Cycle 4, C7, C11, C15, and at EOT (a time window of -7 days is acceptable). For Cycle 2 Day 1, echocardiography may be performed within 72 hours prior to drug administration.
35. If the patient stops trial treatment prior to completion of maximum number of cycles for a reason other than PD, the tumour assessment according to RECIST will be performed according to standard of care until the last follow-up needed according to protocol.
36. A slit-lamp examination will be performed by an ophthalmologist at screening, at the 30-day safety follow-up, and at any time during the treatment period, if clinically indicated. Opacities as seen on clinical slit-lamp examination will be graded according to LOCS III.
37. Although echocardiography is the preferred method, MUGA scans are permitted to quantify LVEF. The same method should be used in a single patient throughout the trial.

[figure not shown]
BLOOD SAMPLE FLOW CHART: ARM A

BLOOD SAMPLE FLOW CHART: ARM A (cont.)

[figure not shown]

BLOOD SAMPLE FLOW CHART: ARM A (cont.)

[figure not shown]

1. Only if patient discontinues before Cycle 4

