## 6. GENERAL ANALYSIS DEFINITIONS

## 6.1 TREATMENT(S)

In this Phase I trial treatments are not randomized. In Arm A and Arm B, different dose levels of BI 1387446 alone (Arm A) or of BI 1387446 in combination with 240 mg of ezabenlimab (Arm B) are being administered.

If not specified otherwise, all analyses will be performed for each treatment arm separately. Data will be presented by initial treatment, i.e. within each treatment arm for all dose cohorts separately and in total over all dose cohorts of that arm.

For safety summaries, events that start from the first administration of any trial medication until 90 days after the last administration of any trial medication (residual effect period, REP) will be assigned to the on-treatment period for evaluation. If not specified otherwise, all safety tables will be based on the on-treatment period. Adverse events that have an onset during the screening or the follow-up period will be displayed in separate listings from those that occurred during the on-treatment period.

The MTD evaluation period will be derived as the time from the first administration of study drug to the start of the second treatment cycle, i.e., in more detail as the time from the first administration of (any) trial medication to the start of the 2nd administration of ezabenlimab or 4th administration of BI 1387446 (whatever from the latter two comes first). In the case that the 2nd administration of ezabenlimab and/or the 4th administration of BI 1387446 are not given, the MTD evaluation period ends 90 days after the last administration.

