#### • Treated set (TS):

This patient set includes all patients who were documented to have received at least one dose of any study medication. The treated set will be used for all demographic and baseline analyses as well as all safety and efficacy analyses (besides the MTD determination).

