#### 7.8.1 Adverse Events

Date: 8 Apr 2024, Version 1.0

The analyses of AEs will be descriptive in nature. All analyses of AEs will be based on the number of subjects with AEs and NOT on the number of AEs. The analysis will be based on BI standards (9.6). AEs will be coded using the most recent version of MedDRA. The severity of AEs will be scaled according to the Common terminology Criteria for Adverse Events (CTCAE) version 5.0.

The analysis of AEs will be based on the concept of treatment emergent AEs. That means that all AEs occurring between first administration of trial medication until 90 days after last administration of trial medication will be considered treatment-emergent and assigned to the initial planned treatment.

All AEs occurring before first administration of trial medication will be assigned to 'screening' and all AEs occurring after last administration of trial medication + 90 days will be assigned to 'follow-up' (for listings only). For details on the treatment definition, see Section 6.1.

AEs will be reported with start day and end day as calculated from the first day of treatment with trial medication. For listings displaying AEs during the screening or follow-up period, the start and stop day are calculated from the start of the respective analysis period.

Proprietary confidential information © 2024 Boehringer Ingelheim International GmbH or one or more of its affiliated companies.

An overall summary of AEs will be presented.

AEs will be displayed by the initial planned dose of trial medication administered on the first day of treatment. Patients who undergo a cross-over from Arm A to Arm B during the trial will be displayed in both treatment arms: by the initial planned dose of study medication in Arm A and by the planned combination dose in Arm B.

The frequency of patients with AEs during the on-treatment period will be summarized by treatment, primary system organ class (SOC) and preferred term (PT) for each of the following AE tables:

The frequency of patients with AEs during the on-treatment period will be summarized by treatment, primary system organ class (SOC) and preferred term (PT) for each of the following AE tables:

- DLTs
- All AEs by highest CTCAE grade
- Serious AEs by highest CTCAE grade
- Investigator assessed BI 1387446 related AEs by highest CTCAE grade
- Investigator assessed ezabenlimab related AEs by highest CTCAE grade
- Investigator assessed BI 1387446 related SAEs by highest CTCAE grade

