- Investigator assessed ezabenlimab related SAEs by highest CTCAE grade
- Investigator assessed Adverse Events of Special Interest (AESI) by highest CTCAE grade
- Investigator assessed infusion-related AEs by highest CTCAE grade
- Investigator assessed immune-related AEs by highest CTCAE grade
- Investigator assessed procedural complication (biopsy/injection) AEs by highest CTCAE grade
- AEs leading to treatment discontinuation of BI 1387446 by highest CTCAE grade
- AEs leading to treatment discontinuation of ezabenlimab by highest CTCAE grade
- AEs leading to dose reduction of BI 1387446 by highest CTCAE grade
- AEs leading to death

The SOC will be sorted alphabetically, preferred terms will be sorted by frequency (within SOC).

Listings of DLTs, fatal AEs, serious AEs, AEs leading to treatment discontinuation of BI 1387446, AEs leading to treatment discontinuation of ezabenlimab and AEs leading to dose reduction of BI 1387446 will be provided.

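### The biopsy/injection complication table in SAP 7.8.1 counts only events that start after first dose in treated patients, so complications of the two mandatory baseline biopsies that begin before dosing are missing from the reported frequency

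*SAP*

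**What the plan says.** SAP 7.8.1 lists the adverse event tables to be produced. One is "Investigator assessed procedural complication (biopsy/injection) AEs by highest CTCAE grade". The sentence introducing the list sets the window for all of them: "The frequency of patients with AEs during the on-treatment period will be summarized by treatment". SAP 6.1 defines that period as covering "events that start from the first administration of any trial medication until 90 days after the last administration of any trial medication". For anything earlier or later it says: "Adverse events that have an onset during the screening or the follow-up period will be displayed in separate listings".

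The population is fixed in SAP 6.4: "The treated set will be used for all demographic and baseline analyses as well as all safety and efficacy analyses", with MTD determination as the exception. Membership requires at least one dose. SAP 7.8 repeats this for safety. The screened set is assigned only to disposition tables.

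The biopsy schedule is in the protocol's Arm A and B flow chart. Footnote 28 states: "Mandatory timepoints are baseline and C2D1". Footnote 21 places the baseline sample, from the lesion projected for injection and one separate non-injected lesion, "between screening and first administration of BI 1387446". Protocol 5.2.7.2.1 collects all adverse events from consent onwards.

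**The concern.** Counting from first dose suits drug-related events, because exposure to the drug starts there. Exposure to biopsy risk starts at the first study biopsy. The SAP applies the drug's starting point to a table whose title names biopsy, and gives no caveat.

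Protocol 1.4.2 treats biopsy as carrying procedural risks similar to those of intratumoural injection, and allows lung biopsies when lower-risk sites are unavailable. A reader of the study report would naturally take this table as the trial's biopsy complication frequency. It leaves out events that begin and are recognised between the first round of mandatory biopsies and first dose, which is when an immediate bleed or tissue injury would show. If such an event stops treatment from starting, the patient is not in the population at all.

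**Working it through.** The SAP gives no figure to reproduce, so the check traces the definitions and then counts procedures.

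**Inputs**
- Table and window: SAP 7.8.1 and 6.1, by date of onset, starting at first administration of any trial medication.
- Population: treated set (SAP 6.4 and 7.8).
- Mandatory biopsies: 2 lesions at baseline and Cycle 2 Day 1 (flow chart footnotes 21 and 28). Protocol 5.4.1 makes pre-treatment and on-treatment biopsies mandatory for all patients.
- Planned size: approximately 78 patients (protocol synopsis).

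**Where each kind of event goes**

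| Event | Frequency table | Elsewhere |
|---|---|---|
| Baseline biopsy complication, onset before first dose, patient later dosed | No | Screening listing |
| Same, patient never dosed | No | No adverse event output clearly assigned |
| Baseline biopsy complication, onset after first dose | Yes | – |
| Onset before first dose, worsens on treatment | Yes under protocol 7.2.5; the SAP does not repeat the rule | – |
| Cycle 2 Day 1 and optional on-treatment biopsies | Yes | – |
| New biopsies before cross-over to Arm B | Generally yes, in the Arm A window | – |
| Injection complications | Yes | – |

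**Count of mandatory biopsies**
- Per patient: 2 lesions × 2 timepoints = 4.
- Before first dose: 2 lesions × 1 timepoint = 2, so 2/4 = 50%.
- For 78 patients with full compliance: 78 × 4 = 312 procedures, of which 78 × 2 = 156 precede the window.

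**Direction.** Among treated patients the omission can only lower the number with a biopsy complication, or leave it unchanged if the patient is counted for another event. Leaving out undosed patients removes them from both numerator and denominator. What is lost for certain is any case where the complication itself prevented dosing.

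**Size.** Neither document states a complication rate per biopsy, so the number of events omitted cannot be calculated.

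**The case against.** The strongest reply is that the SAP does what the protocol asks. Protocol 7.2.5 centres adverse event reporting on treatment-emergent events in treated patients, and the same window applies to every table in the list. Screening-onset events are still listed case by case, which is informative in an open-label trial of about 78 patients. The table serves no primary or secondary endpoint. Undosed patients also have no dose cohort in which to appear. All of this stands. It argues for leaving the on-treatment table as it is and adding a separate summary, but it does not put the missing biopsy round into any frequency.

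Three stronger readings are tempting, and the documents do not support them.

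- A reader might infer that the table captures at most half of the biopsy complications. The 2 of 4 counts mandatory procedures, not events. Assignment is by onset, so a baseline-biopsy infection that appears after dosing is counted, and so are optional and cross-over biopsies.
- A reader might infer that the reported percentage is halved. With an assumed, independent 5% risk per biopsy, four mandatory biopsies give 1 − 0.95^4 = 18.5%, against 1 − 0.95^2 = 9.8% for two. But the table also includes injections: three in Cycle 1 (protocol 4.1.4.6), with the fourth marking Cycle 2 (SAP 5.1). With the same 5% for all 8 procedures through Cycle 2 Day 1, the contrast is 1 − 0.95^8 = 33.7% against 1 − 0.95^6 = 26.5%, and the excluded share is 2 of 8 (25%). The 5% comes from neither document, so neither contrast estimates this trial's shortfall.
- A reader might infer that the protocol lists biopsy among the main risks. The list in protocol 1.4.2 names procedural risk from intratumoural application only. Biopsy appears in a later sub-heading and in its own paragraph.

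**Conclusion.** The point holds for the frequency table. Complications of the two baseline biopsies that start before first dose are collected but not summarised by frequency and grade, and undosed biopsied patients are outside the analysis population. The biopsy complication frequency is understated by an unknown amount. The firm figure is that 2 of the 4 mandatory biopsies per patient fall before the window.

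Two assumptions lie behind this. First, that baseline biopsies precede all trial drug: footnote 21 refers to the first BI 1387446 dose, while the window opens with whichever drug is given first. Second, that the screening listing follows the treated set, since SAP 6.1 names no other population for it. Few patients may be biopsied and never dosed, because footnote 21 limits the procedure to those already judged eligible.

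It would be wrong to infer that these events vanish from the report: for treated patients they are listed. No hypothesis test is planned, and the MTD is determined from DLTs in the MTD set, so this table does not enter it. The change is worth making because procedural risk is one the protocol sets out to monitor, and the data are already in hand.

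**What to change.** In SAP 7.8.1:

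1. Keep the on-treatment procedural complication table by dose cohort. State in its title that it covers onset after first dose, and show biopsy and injection complications separately.
2. Add one summary by CTCAE grade of biopsy complications with onset from first study biopsy to first dose, or to end of participation for patients never dosed. Use all patients who had a study biopsy as the denominator, without splitting by dose cohort.
3. State that the screening adverse event listing includes patients who were biopsied but never dosed.
4. Reconcile the SAP with protocol 7.2.5 on events that start before first dose and worsen under treatment, so that it is clear whether they enter the on-treatment table.

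The cost is SAP wording and one extra descriptive table whose denominator differs from the other safety tables and should be footnoted. No new data collection is needed, because adverse events are recorded from consent.

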#### 7.8.2 Laboratory data

Date: 8 Apr 2024, Version 1.0

The analysis of laboratory data will be descriptive in nature and will be based on BI standards (9.7). The same on-treatment period as considered for the analysis of AEs will be applied for laboratory values. Patients having at least one post-baseline laboratory value will be displayed in the descriptive analyses.

Proprietary confidential information © 2024 Boehringer Ingelheim International GmbH or one or more of its affiliated companies.

CTCAE grades for applicable laboratory parameters will be calculated according to CTCAE v5.0. Patients with missing CTCAE grade at baseline or no baseline value but with post-baseline values will be displayed as "Missing" for those laboratory parameters where CTCAE grading is applicable. For some laboratory parameters which cannot be assigned a CTCAE grade at baseline, CTCAE shift tables will be replaced by shift tables of pre-defined categories based on Upper Limit of Normal (ULN) values. A similar approach will also be adopted for creatinine due to the ambiguity of CTCAE grading for grade 2 and 3. The predefined categories will follow BI standards (9.8).

#### The following outputs will be presented:

- Descriptive statistics, including baseline and change from baseline
- Frequency of patients with shifts from baseline:
  - o Transitions of CTCAE grade from baseline to worst laboratory value,
  - o Transitions of CTCAE grade from baseline to last laboratory value
- Frequency of patients with possible clinically significant abnormalities (according to the BI standard definitions)

### Possible clinically significant abnormal laboratory values:

Possible clinically significant abnormal laboratory values are defined as those laboratory values that are of CTCAE grade  $\geq 2$  and show an increase from baseline value by at least one CTCAE grade. For those parameters for which no CTCAE grade has been defined, BI standard definitions will be used to determine possible clinical significance. Frequency of patients with possible clinically significant abnormal laboratory values will be provided whenever applicable. If no baseline value is available (or CTCAE grading at baseline cannot be assigned) but the patient has a post-baseline laboratory value of CTCAE grade  $\geq 2$ , an increase from baseline will be assumed, i.e. the laboratory value will be considered as possibly clinically significant.

#### Corrected calcium:

Date: 8 Apr 2024, Version 1.0

The grading of hypocalcaemia is based on corrected calcium as calcium can be falsely low if hypoalbuminemia is present. The following corrective calculation will be performed: Corrected calcium (mg/dL) = Total Calcium (mg/dL) – 0.8[Albumin (g/dL)-4]

No correction of the reference range has to be done. The reported reference range of total calcium will be used for analyses. Corrected calcium can be only derived at a certain time point in case both laboratory values total calcium and albumin have been reported for the patient in the same laboratory sample.

#### Hepatic enzyme elevations (potential Hy's law cases):

These are defined as those cases where a combination of all of the following events occurred: any on-treatment value of ALT and/or AST > 3ULN (upper limit of normal) with total bilirubin  $\geq$  2ULN and ALKP < 2ULN. The events can occur in any order, but must occur within 30 days of the previous event, i.e. the second event must occur within 30 days of the first event, and the third event must occur within 30 days of the second event, etc. Patients with missing laboratory values for liver enzymes will be excluded from these analyses, but presented separately.

Proprietary confidential information © 2024 Boehringer Ingelheim International GmbH or one or more of its affiliated companies.

A listing of patients with hepatic injuries according to CTP Section 5.2.7.1.4 will be provided.

## 7.8.3 Vital signs

Only descriptive statistics are planned for this section of the report.

[figure not shown]
#### 7.8.4 ECG

Analyses of ECG will be descriptive in nature. Newly emergent abnormalities will be recorded and analyzed as adverse events. As outlined in Section 4, centrally evaluated ECG recordings will not be analyzed.

#### 7.9 OTHER ANALYSIS

Proprietary confidential information © 2024 Boehringer Ingelheim International GmbH or one or more of its affiliated companies.

## 7.9.3 Eastern Cooperative Oncology Group performance status

Date: 8 Apr 2024, Version 1.0

The best, worst and last ECOG performance status during treatment will be summarized by dose cohort and baseline ECOG status.

Date: 8 Apr 2024, Version 1.0

c44138015-01

Proprietary confidential information © 2024 Boehringer Ingelheim International GmbH or one or more of its affiliated companies.

## 8. TIMEPOINT OF RELEASE OF TREATMENT INFORMATION

The treatment information will be loaded into the trial database at trial initiation.

Proprietary confidential information © 2024 Boehringer Ingelheim International GmbH or one or more of its affiliated companies.

# 11. HISTORY TABLE

Table 11:1 History table

Version	Date (DD-MMM- YY)	Author	Sections changed	Brief description of change
1.0	08-APR-24		None	This is the final TSAP.
